Appendix III contains a list of common medications that should be avoided or used with caution.

Regarding Covid-19 vaccination, as setanaxib does not have immunosuppressive properties based on nonclinical and clinical safety data, and as the available literature and expert assessment concludes that patients taking pembrolizumab and other immune checkpoint inhibitors should be considered for Covid-19 vaccination, the sponsor considers that study patients may undergo Covid-19 vaccination during the study. All approved Covid-19 vaccines are allowed in setanaxib studies and are to be recorded as a concomitant medication. It is important that the Covid-19 vaccinations are not delayed.

If patients receive a prohibited medication, investigators should consider whether IMP administration should be temporarily interrupted or permanently discontinued. Additionally, if a patient has taken a prohibited medication (eg, short-term antifungal therapy) and the investigator learns about it later, this might not lead to the permanent discontinuation of IMP.

All medication (including vaccines, over-the-counter or prescription medicines, vitamins, and/or herbal supplements) taken from 3 months (90 days) before Screening Visit until the end of the Safety/Efficacy Follow-up Period will be recorded in the appropriate section of the eCRF.

The following details must be recorded in the eCRF:

- Medication name, ideally the generic and/or brand names
- Reason for use
- Start and end date of administration
- The dose, route and frequency of administration

The medical monitor should be contacted if there are any questions regarding prior or concomitant medication or procedures.

For patients who discontinued study treatment but remain followed for tumour assessment until RECIST v1.1-defined disease progression, any further anti-cancer medication will be recorded until progression.

6.9 Overdose

For this study, a single intake of 5 or more setanaxib tablets and/or a total daily dose of 7 or more tablets will be considered an overdose.

The sponsor does not recommend specific treatment for an overdose with setanaxib.

Decisions regarding dose interruptions will be made by the investigator based on the clinical evaluation of the patient.

In the event of an overdose, patients should be closely observed/hospitalised for close observation and appropriate symptomatic/supportive medical care and be followed until resolution/stabilisation of any clinical issues.

Any instance of overdose (suspected or confirmed and irrespective of whether or not it involved setanaxib) must be communicated to the sponsor (or a specified designee) using the overdose report form within 24 hours of becoming aware of its occurrence, using the contact details provided.

Any overdose associated with clinical symptoms will be recorded as an AE or SAE, as appropriate. Note that an overdose without clinical symptoms will not be recorded as an AE or SAE, even if the patient was hospitalised for observation. Details of any signs or symptoms and their management should be recorded, including details of any treatments

administered for the overdose. All overdoses with clinical symptoms meeting the SAE criteria must be reported as described in Section 7.4.

6.10 Compliance

The investigator (or designee) will explain the correct use of the IMP to each patient and will check that each patient is following the instructions properly. Patients will document the IMP doses that they take on a patient IMP dosing card.

Compliance will be assessed by counting the returned tablets and will be documented in the source documents and eCRF. Any deviation from the correct use of the IMP will be recorded in the eCRF.

A record of the number of IMP tablets dispensed to and taken by each patient will be maintained and reconciled with IMP and compliance records. The IMP start and stop dates, including dates for IMP interruptions, will also be recorded in the eCRF.

6.11 Accountability

The IMP must not be used for any purpose other than that defined in this protocol. All supplies of IMP will be accounted for in accordance with Good Clinical Practice (GCP).

The pharmacist or (designee) should maintain accurate records of all IMP supplies received during the study. These records should include the dates and amounts of IMP that were received at the site, dispensed, and destroyed or returned to the sponsor (or designee). The records should include dates, quantities, batch/serial numbers, expiration dates (if applicable), and the unique code numbers assigned to the IMP and study patients. If errors or damage in the IMP shipments occur, the investigator should contact the sponsor (or its designee) immediately. Copies of the IMP accountability records will be provided by each investigator for inclusion in the trial master file. The study monitor will periodically check the supplies of IMP held by the investigator or pharmacist to verify accountability of the IMP used.

The investigator (or designee) will dispense the IMP only to the identified and randomised patients in this study, according to the procedures described in this study protocol. Details of IMP dispensed to patients will be recorded in the eCRF. Investigators should maintain records that document adequately that the patients were provided the doses specified by the protocol and reconcile all IMP received from the sponsor (or designee). Patients will be reminded to bring the IMP with them to each study visit. Details of returned IMP will be recorded in the eCRF and accountability records.

After the end of the study, all unused IMP and all medication containers should be destroyed at the study centre or returned to the drug depot for destruction, as instructed in the pharmacy manual. In either instance, complete documentation will be returned to the sponsor (or designee). The IMP resupply will be managed by the IRT.

7 ADVERSE EVENTS

7.1 **Definitions**

7.1.1 Adverse Events

An AE is any untoward medical occurrence in a patient or clinical study patient administered a pharmaceutical product and that does not necessarily have a causal relationship with this treatment. An AE can, therefore, be any unfavourable and unintended sign (including an abnormal laboratory finding), symptom, or disease temporally associated with the use of a medicinal (investigational) product, whether or not related to the medicinal (investigational) product.

AEs that occur, having been absent before the date and time of the first dose of the IMP, or having worsened in severity or seriousness after initiating the IMP until 28 days after the date and time of last dose of IMP, will be classified as TEAEs.

An event solely attributed to tumour progression should not be reported as an AE, unless the signs and symptoms of the event are more severe than expected for the patient's condition. If the criteria for an AE is not met, disease progression will be recorded as efficacy data. Any event that meets one or more of the seriousness criteria will be reported as an SAE per the procedures outlined in Section 7.4.

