7.1.2 Serious Adverse Events

An SAE is any event that meets any of the following criteria:

- Results in death (investigators should identify 1 SAE that is the leading cause of death).
- Is life-threatening.
- Requires inpatient hospitalisation or prolongation of existing hospitalisation.
- Results in persistent or significant disability/incapacity.
- Is a congenital anomaly/birth defect.
- Is an important medical event that may not result in death, be life-threatening, or require hospitalisation. The event will be considered an SAE when, based upon appropriate medical and scientific judgment, the event may jeopardise the patient and may require medical or surgical intervention to prevent one of the outcomes listed above. Examples of such events include: intensive treatment in an emergency room or at home for allergic bronchospasm, blood dyscrasias or convulsions that do not

result in inpatient hospitalisation, or the development of drug dependency or drug abuse.

Definition of Terms

Life-threatening: an AE is life-threatening if the patient was at immediate risk of death from the event as it occurred; ie, it does not include a reaction that, if it had occurred in a more severe form, might have caused death. For example, drug-induced hepatitis that resolved without evidence of hepatic failure would not be considered life-threatening even though drug-induced hepatitis can be fatal. It does not include an AE or suspected adverse reaction that, had it occurred in a more severe form, might have caused death.

Hospitalisation: AEs requiring hospitalisation should be considered SAEs. Hospitalisation for elective surgery, or for procedures planned prior to the patient providing informed consent, or routine clinical procedures that are not the result of an AE (eg, elective surgery for a pre-existing condition that has not worsened) need not be considered AEs or SAEs. If anything untoward is reported during the procedure, that occurrence must be reported as an AE, either 'serious' or 'nonserious' according to the usual criteria.

In general, hospitalisation signifies that the patient has been detained (usually involving at least an overnight stay) at the hospital or emergency ward for observation and/or treatment that would not have been appropriate in the physician's office or outpatient setting. When in doubt as to whether hospitalisation occurred or was necessary, the AE should be considered serious.

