7.3 Documenting and Reporting Adverse Events

Reporting of AEs will begin when the patient has provided informed consent and will continue up to the 28 days after the last IMP administration.

Occurrence of AEs may be volunteered spontaneously by the patient; discovered as a result of general, nonleading verbal questioning by the study staff; or determined by physical examination or other safety assessments. All AEs will be monitored and recorded in the eCRF throughout the entire study. Note that worsening of SCCHN-related pre-existing conditions, including disease progression, will not be reported as AEs. An event solely attributed to tumour progression should not be reported as an AE, unless the signs and symptoms of the event are more severe than expected for the patient's condition. If the criteria for an AE is not met, disease progression will be recorded as efficacy data. Worsening of other existing abnormalities that are associated with signs and/or symptoms should be reported as AEs (or SAEs), as appropriate. Any event that meets one or more of the seriousness criteria will be reported as an SAE per the procedures outlined in Section 7.4.

For all AEs, the investigator must pursue and obtain adequate information (a description of the event, severity, time of occurrence, including whether the AE onset was before, during, or after the IMP administration if the AE started on a dosing day, duration, and any action, eg, treatment/follow-up tests). The outcome of the event should be provided along with the investigator's assessment of the relationship to the IMP. The investigator must also assess whether the event meets the criteria for classification as an SAE.

It is the investigator's responsibility to review all documentation (eg, hospital notes, laboratory reports, and diagnostic reports) related to an AE. Wherever possible, the investigator's diagnosis, not the individual signs and symptoms, will be documented as the AE.

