12.6.2 Deaths and Serious Adverse Events

A summary of serious TEAEs by SOC, PT, and maximum severity will also be presented by patient (not events). Patients can experience multiple events within the same SOC/PT, they will be counted only once in the most severe grade.

The following types of TEAEs will also be summarised by SOC and PT:

- Serious TEAEs
- Serious TEAEs Related to IMP
- TEAEs with a Fatal Outcome

Separate listings will be provided for all SAEs and all AEs with a fatal outcome.

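### Protocol 7.1.1 and 7.3 exempt progression events from AE reporting, then make any event meeting a seriousness criterion an SAE; no rule says which prevails, and the SAP's serious and fatal TEAE totals inherit the ambiguity

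*Protocol*

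**What the plan says.** Protocol 7.1.1 first sets an exemption: "An event solely attributed to tumour progression should not be reported as an AE, unless the signs and symptoms" exceed what is expected for that patient. It then says where exempt events go: "If the criteria for an AE is not met, disease progression will be recorded as efficacy data". The sentence that follows reads: "Any event that meets one or more of the seriousness criteria will be reported as an SAE per the procedures outlined in Section 7.4".

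Section 7.3 repeats this sequence and precedes it with a broader statement: "Note that worsening of SCCHN-related pre-existing conditions, including disease progression, will not be reported as AEs".

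Section 7.1.2 opens with "An SAE is any event that meets any of the following criteria". Two of its criteria matter here. One is "Requires inpatient hospitalisation or prolongation of existing hospitalisation". The other begins "Results in death (investigators should identify 1 SAE that is the leading cause of death", and the parenthesis closes there. Neither mentions progression.

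Sections 5.3.7 (physical examination) and 7.1.4 (laboratory and other abnormal assessments) except head and neck cancer-related pre-existing conditions, disease progression included, from reporting either as AEs or as SAEs. Section 7.1.4 refers the reader to Section 7.3.

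SAP 10.10.1 defines a TEAE by whether the record is an AE. SAP 12.6.1 and 12.6.2 count serious TEAEs and "TEAEs with a Fatal Outcome" from those records. The SAP's list of changes and clarifications (Section 6.1) has no entry on progression events.

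**The concern.** Take a patient who dies of progression, or is admitted because of it, while still inside the reporting window. One sentence sends the event to the efficacy data only. The next, which says event and not adverse event, sends it to SAE reporting. An investigator can justify either course from the text.

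This matters because progression is itself an efficacy outcome, and the trial is designed around a PFS hazard ratio of 0.5. If progression events count as SAEs, the arm that progresses faster shows more serious and fatal TEAEs even when the drugs are equally safe. If they do not count, that difference disappears. With about 25 patients per arm and descriptive safety tables, a few patients change the picture.

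The problem is realistic in this disease. Protocol 1.1.3 lists the treatment-related deaths in a phase 3 pembrolizumab trial in previously treated patients: malignant neoplasm progression is one of four on pembrolizumab and one of two on standard of care.

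**Working it through.** **Step 1: the texts side by side**, for progression that is fatal or leads to admission.

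| Section | Scope | AE? | SAE? |
|---|---|---|---|
| 7.1.1, 7.3 (exemption) | events due only to progression | no, unless worse than expected | not stated |
| 7.1.1, 7.3 (last sentence) | any event | not stated | yes |
| 7.1.2 (criteria) | any event | not stated | yes |
| 7.1.2 (explanation of hospitalisation) | AEs requiring admission | presupposed | only if an AE |
| 5.3.7, 7.1.4 | examination findings; abnormal assessments | no | no |

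No section ranks these rules.

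**Step 2: into the SAP.** A record reaches the serious or fatal TEAE table only if the site entered it as an AE. The SAP has no rule to include, exclude or separately total progression records, so the protocol ambiguity passes straight into the tables.

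**Step 3: reproduce the plan's event count**, the only stated figure that gives a scale. Schoenfeld's formula with hazard ratio 0.5, two-sided alpha 0.2, power 0.8 and 1:1 allocation gives 4 × (1.2816 + 0.8416)² / (ln 0.5)² = 4 × 4.508 / 0.4805 = 37.5, so 38 events. Power at 38 events is 80.4%. The plan's figure holds.

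**Step 4: illustrate the size.** The share q of progression events that are fatal or lead to admission inside the reporting window is not in the documents. It is assumed at 10%, 25% and 50%. All 38 events are placed among 50 patients.

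Split by arm: let x be the setanaxib proportion progression-free. With equal follow-up and a hazard ratio of 0.5, the placebo proportion is x². Then 25(1 − x) + 25(1 − x²) = 38, so x + x² = 0.48 and x = (−1 + √2.92)/2 = 0.354. That gives 25 × 0.646 = 16.1 events on setanaxib and 25 × 0.874 = 21.9 on placebo. The arms differ by (21.86 − 16.14)/25 = 22.9 percentage points before multiplying by q.

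| q (assumed) | Patients moved, 38 × q | Share of 50 | Extra on placebo, 22.9 × q |
|---|---|---|---|
| 10% | 3.8 | 8% | 2 points |
| 25% | 9.5 | 19% | 6 points |
| 50% | 19 | 38% | 11 points |

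**Step 5: the window.** Section 7.4 takes SAEs of any cause only up to the EoT Visit, and after that only those related to IMP. Treatment stops at progression and the EoT Visit follows as soon as possible. Section 7.3 collects AEs to 28 days after the last dose, but does not clearly bring later unrelated SAEs back. Many progression deaths and admissions would fall outside under either reading, so the higher values of q are unlikely.

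**The case against.** The strongest reply is that the text does have an order: a general exemption, then a mandatory override. On that view non-serious progression is efficacy data and serious progression is an SAE, which fits the any-event definition in 7.1.2. Sections 5.3.7 and 7.1.4 are about examination findings and abnormal assessments, and 7.1.4 points back to 7.3, where the override stands. This is a fair reading, and a reader who infers that the two instructions are flatly irreconcilable goes too far. It remains only one reading: 5.3.7 and 7.1.4 name SAEs expressly in their exception, and nothing says that the later sentence governs.

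Second, the SAP already gives partial separation. Serious and fatal TEAEs are tabulated by preferred term, so coded progression has its own row. All SAEs and all fatal AEs are listed. Protocol 7.2.2 classes events explained by the disease under study as not related, so most progression should drop out of the IMP-related serious table. All of this stands. What remains is the totals, fatal TEAEs not split by relatedness, and progression recorded only as symptoms.

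Third, any shift is small against sampling error. At q = 25% the rates are 16.1% and 21.9%, and the standard error of their difference is √(0.161 × 0.839/25 + 0.219 × 0.781/25) = 11.1 points, about twice the 6-point gap. This is true, but the shift is systematic and linked to efficacy, so it is worth removing when the cost is low.

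Fourth, the claim that the IDMC could not interpret the data is not supported. It is unblinded and works from its own Charter and IDMC SAP, neither of which is available here. Nor do the documents show that sites differ in practice; that is an inference from the missing rule.

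**Conclusion.** The concern holds as an ambiguity to be reconciled. Five protocol sections bear on fatal or hospitalised progression without stating which rule prevails, and the SAP does not settle it. The serious and fatal TEAE totals can include or omit these events depending on the reading, and including them adds more to the arm that progresses faster. PFS and OS count progression and death however AEs are recorded, so they are unaffected.

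The size cannot be derived from the documents. The range of about 4 to 19 of 50 patients rests on an assumed 10% to 50% share, and the arm split also rests on the design hazard ratio. Section 7.4 points to the lower part of that range.

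A reader might infer a firmer gap from Section 3.2: if about 30% remain on setanaxib at 12 months and the hazard ratio is 0.5, then 70% and 91% progress (0.30² = 0.09), and a 15% to 30% serious share gives a gap of 3 to 6 points. The documents do not support this as an estimate. Section 3.2 anticipates treatment duration, not PFS, and patients stop for other reasons. The share has no source. Counting to 28 days after the last dose overruns the window in 7.4. Nor does the 8% of patients with AEs leading to death on pembrolizumab alone (Section 1.1.3) give a scale, since that figure is fatal events only.

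One limit applies throughout: the protocol reviewed is version 4.0, whereas the SAP cites version 5.0, which was not available.

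**What to change.** **Protocol.** Reconcile 7.1.1, 7.1.2, 7.3, 5.3.7 and 7.1.4 so that one stated rule covers progression that is fatal or leads to admission, including how the instruction to name one SAE as the cause of death applies. Keep the exception for events worse than expected consistent for AEs and SAEs. Simply exempting every event due only to progression from SAE reporting would break this: an unexpectedly severe fatal event would be an AE but not an SAE. The documents support reconciliation; they do not settle whether the narrower or the wider rule is right. First confirm the wording in protocol version 5.0.

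**SAP 12.6.1 and 12.6.2.** Present the serious and fatal TEAE totals both with and without MedDRA disease-progression terms. This makes the tables readable whichever rule sites followed, and can be done even if a protocol amendment comes too late.

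**Cost.** A short protocol edit, a SAP sentence, a few table rows, and a flag for progression events already reported as SAEs. Progression recorded only as symptoms will not be caught by the terms, and the SAP should say so.

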7.1.2 Serious Adverse Events

An SAE is any event that meets any of the following criteria:

- Results in death (investigators should identify 1 SAE that is the leading cause of death).
- Is life-threatening.
- Requires inpatient hospitalisation or prolongation of existing hospitalisation.
- Results in persistent or significant disability/incapacity.
- Is a congenital anomaly/birth defect.
- Is an important medical event that may not result in death, be life-threatening, or require hospitalisation. The event will be considered an SAE when, based upon appropriate medical and scientific judgment, the event may jeopardise the patient and may require medical or surgical intervention to prevent one of the outcomes listed above. Examples of such events include: intensive treatment in an emergency room or at home for allergic bronchospasm, blood dyscrasias or convulsions that do not

result in inpatient hospitalisation, or the development of drug dependency or drug abuse.

Definition of Terms

Life-threatening: an AE is life-threatening if the patient was at immediate risk of death from the event as it occurred; ie, it does not include a reaction that, if it had occurred in a more severe form, might have caused death. For example, drug-induced hepatitis that resolved without evidence of hepatic failure would not be considered life-threatening even though drug-induced hepatitis can be fatal. It does not include an AE or suspected adverse reaction that, had it occurred in a more severe form, might have caused death.

Hospitalisation: AEs requiring hospitalisation should be considered SAEs. Hospitalisation for elective surgery, or for procedures planned prior to the patient providing informed consent, or routine clinical procedures that are not the result of an AE (eg, elective surgery for a pre-existing condition that has not worsened) need not be considered AEs or SAEs. If anything untoward is reported during the procedure, that occurrence must be reported as an AE, either 'serious' or 'nonserious' according to the usual criteria.

In general, hospitalisation signifies that the patient has been detained (usually involving at least an overnight stay) at the hospital or emergency ward for observation and/or treatment that would not have been appropriate in the physician's office or outpatient setting. When in doubt as to whether hospitalisation occurred or was necessary, the AE should be considered serious.

Disability/incapacity: an AE is incapacitating or disabling if the experience results in a substantial and/or permanent disruption of the patient's ability to carry out normal life functions.

